9.5.2.1 Primary Endpoint

The primary efficacy endpoint is the proportion of participants who achieve a ≥ 1 -stage improvement (as defined by NASH CRN Fibrosis Score) in fibrosis without worsening of NASH or NASH improvement (as defined by NAFLD Activity Score) with no worsening of fibrosis (as defined by NASH CRN Fibrosis Score) at Week 24, as determined by liver biopsy.

For this protocol, improvement in fibrosis is defined as a decrease of fibrosis by ≥ 1 point, as determined by the NASH CRN Fibrosis Score. Worsening of fibrosis is defined as an increase of fibrosis by ≥ 1 point, as determined by the NASH CRN Fibrosis Score.

Worsening of NASH is defined as an increase of the NAFLD Activity Score (NAS) by ≥ 1 point. NASH improvement is defined as a decrease of NAS by ≥ 2 points (with contribution from > 1 NAS component) (see [Section 8.5.1.1](#)).

Stratification will be defined as follows: One of the strata will have participants from Japan and the other four will correspond to sites in other countries 1: T2DM status (yes) and NAS (≤ 5); 2: T2DM status (yes) and NAS (> 5); 3: T2DM status (no) and NAS (≤ 5); 4: T2DM status (no) and NAS (> 5).

A Cochran-Armitage trend test across proportions at a one-sided 0.05 level of significance will be used to examine the linear trend among the proportions across treatment groups. Also, 95% CIs for the odds-ratio of each BMS treatment group to placebo will be provided.

A sensitivity analysis using an extended Cochran Mantel-Haenszel (CMH) correlation test³⁶ will be used to assess the trend among the proportions for treatment groups with an adjustment to strata. A two-sided 0.10 level of significance will be used.

Since this is a Phase 2 study, no adjustment for multiplicity will be applied.

All participants who prematurely discontinue from treatment without a biopsy at Week 24 (or ET, if applicable) or otherwise have a missing Week 24 (or ET, if applicable) biopsy result will be considered nonresponders for the primary analysis of the primary efficacy endpoint. In addition, a completer analysis of the primary endpoint will be performed excluding participants without a Week 24 biopsy.

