6.1.1 Primary Efficacy Analysis

The primary efficacy endpoint is the proportion of participants who achieve a ≥ 1 -stage improvement (as defined by NASH CRN Fibrosis Score) in fibrosis without worsening of NASH or NASH improvement (as defined by NAFLD Activity Score) with no worsening of fibrosis (as defined by NASH CRN Fibrosis Score) at Week 24, as determined by liver biopsy.

For this protocol, improvement in fibrosis is defined as a decrease of fibrosis by ≥ 1 point, as determined by the NASH CRN Fibrosis Score. Worsening of fibrosis is defined as an increase of fibrosis by ≥ 1 point, as determined by the NASH CRN Fibrosis Score. Worsening of NASH is defined as an increase of the

Sponsor: Bristol-Myers Squibb

Protocol no: MB130-068

NAFLD Activity Score (NAS) by ≥ 1 point. NASH improvement is defined as a decrease of NAS by ≥ 2 points (with contribution from > 1 NAS component).

A Cochran-Armitage trend test of proportions at a one-sided 0.05 level of significance will be used to examine the linear trend among the proportions across treatment groups. In addition, 95% confidence intervals (CIs) for the odds-ratio of each BMS treatment group to placebo will be provided. The null hypothesis states that there is no association between treatment groups and fibrosis stage improvement. The alternative hypothesis states that there is an association between treatment groups and fibrosis stage improvement. The Cochran-Armitage trend test does not take into consideration stratification factors into the model therefore, further sensitivity analysis will be performed as described below in SAP Section 6.1.1.1.

The proportion of participants with response will be summarized as frequency counts and percentages by randomized strata as well as overall for each treatment group.

Participants who prematurely discontinue from treatment without a biopsy result for NASH CRN Fibrosis Score or NAS at Week 24 (or ET, if applicable) or otherwise have a missing Week 24 (or ET, if applicable) biopsy result will be considered non-responders for the primary analysis of the primary efficacy endpoint.

The primary analysis will be based on the mITT population. In addition, a completer analysis of the primary variable will be performed. Patients with an evaluable Week 24 biopsy results are considered completers. All biopsy results will be included in the participant listings.

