6.5.5 Protocol Deviations

Important protocol deviations will be summarized by number and percentage of participants experiencing each deviation category. All protocol deviations will be listed and will indicate if the deviation was COVID 19 related.

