7.2 Week 24 Data Analysis

Due to COVID-19 the Week 24 data analysis is based on approximately 160 subjects when planned sample size was reached which occurred at eCRF data cut-off date of May 29 2020. The study will continue to enroll for Week 52 data analysis in a blinded fashion as planned for 197 patients. The level of unblinding and roles to be unblinded will be specified in a separate unblinding study plan that will be finalized prior to the database lock (reference for unblinding plan). The study will continue in a blinded fashion following this analysis. Study data through Week 24 will be analyzed by pre-specified unblinded individuals as specified in the unblinded plan.

- All Efficacy data will be summarized based on mITT principle for DB Lock defined by eCRF date cut-off MAY 29, 2020 on all participants who have completed liver biopsy.
- If the biopsies were delayed and performed between Week 24 and Week 48, the biopsies results will be included in the planned Week 24.
- Safety data will be summarized using Safety population through DB lock defined by eCRF date cut-off May 29, 2020.
- All available data beyond Week 24 will be summarized descriptively.
- SAS datasets and subject level data listings will be shared in accordance with unblinding plan (add reference)

This analysis will include the primary and secondary efficacy endpoints, and selected safety, PK, and exploratory endpoints. The list of tables, figures, and listings (TFLs) to be provided for this analysis will be kept in a separate document outside the SAP.

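### No planned analysis keeps treatment discontinuation as failure while treating biopsies never obtained for unrelated reasons, such as COVID-19, as missing

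*Protocol*

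**What the plan says.** Protocol 9.5.2.1 puts two groups under one rule. Participants who stop treatment without a biopsy, and those who "otherwise have a missing Week 24 (or ET, if applicable) biopsy result will be considered nonresponders for the primary analysis", all count as failures. SAP 6.1.1 carries this over: participants with no "biopsy result will be considered non-responders for the primary analysis of the primary efficacy endpoint". Neither text asks why the biopsy is missing.

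The one alternative is in the same sections. The protocol states that "a completer analysis of the primary endpoint will be performed excluding participants without a Week 24 biopsy". The SAP states "In addition, a completer analysis of the primary variable will be performed" and adds "Patients with an evaluable Week 24 biopsy results are considered completers". The extended CMH test and logistic regression in SAP 6.1.1.1 adjust for strata and do not change the handling of missing biopsies.

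The SAP deals with the pandemic in two places. Section 7.2 says "Due to COVID-19 the Week 24 data analysis is based on approximately 160 subjects" and makes an allowance for late biopsies: "If the biopsies were delayed and performed between Week 24 and Week 48, the biopsies results will be included in the planned Week 24". Section 6.5.5 says "All protocol deviations will be listed and will indicate if the deviation was COVID 19 related". That flag goes to listings and is not used for the primary endpoint.

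**The concern.** A participant who abandons treatment and has no biopsy can reasonably be called a failure. A participant still on drug whose biopsy never took place because of the pandemic has an unknown outcome, and scoring it as failure lowers the arm's response rate for a reason unrelated to the drug. The completer analysis does not isolate this problem. It removes that participant together with everyone who stopped without a biopsy, so it also discards true failures from the arms where they occur.

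If both kinds of missingness are present, the two planned results bracket the quantity of interest and nothing planned explains the gap. Protocol 6.2.1 says that Phase 3 design and dose selection will draw on this study, so arm-level rates matter as well as the trend p-value. SAP 6.1.2 applies the same method to the secondary endpoints.

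**Working it through.** **Inputs.** Protocol 9.1 and SAP 2.2 give response rates of 15%, 20%, 30% and 40% (placebo, 10, 20, 40 mg), a one-sided Cochran-Armitage test at 0.05, 40 per arm planned and 197 randomised (197/4 = 49.25 per arm). The documents do not give trend scores; I use s = 0, 1, 2, 3. They do not give missing fractions either; those below are assumptions.

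**The plan's own figure.** Power = Φ[(d − 1.645√V0)/√V1], with d = Σn·p·(s − s̄), V0 = p̄(1 − p̄)Σn(s − s̄)², V1 = Σn·p(1 − p)(s − s̄)². At 40 per arm:
- d = 40 × 0.425 = 17.0
- V0 = 0.2625 × 0.7375 × 200 = 38.72
- V1 = 40 × 0.9194 = 36.78
- Power = Φ[(17.0 − 1.645 × 6.222)/6.064] = Φ(1.116) = 86.8%

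Simulation gives 87.1%, and scores in mg give 86.1%. The stated figure of at least 80% is reproduced.

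**Case 1: all misses unrelated to outcome, fraction m in every arm.** Non-response scoring gives p(1 − m) on the full arm.

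| m | 40 mg % | Placebo % | Difference, points | Odds ratio | Power, 49.25 per arm |
|---|---|---|---|---|---|
| 0 | 40.0 | 15.0 | 25.0 | 3.78 | 92.3% |
| 5% | 38.0 | 14.25 | 23.75 | 3.69 | 90.5% |
| 10% | 36.0 | 13.5 | 22.5 | 3.60 | 88.6% |
| 20% | 32.0 | 12.0 | 20.0 | 3.45 | 83.9% |

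In this case the completer analysis is unbiased. In 200,000 simulated trials at 49 per arm, with m = 10% and 20%, it returned 15.0/20.0/30.0/40.0%. It loses only precision (power 86.3% at m = 20%).

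**Case 2: a mix.** Assume that 5/5/10/15% discontinue without a biopsy (d, true failures) and that u = 10% of those still on treatment in each arm miss the biopsy for unrelated reasons. The target is the rate p with discontinuers counted as failures.
- Non-response scoring: p(1 − u).
- Completers: p(1 − u)/[(1 − d)(1 − u)] = p/(1 − d).
- Reason-specific, imputing the unrelated misses at the on-treatment rate: p(1 − u) + u(1 − d) × p/(1 − d) = p.

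| Analysis | Placebo/10/20/40 mg, % | 40 mg minus placebo, points | Odds ratio |
|---|---|---|---|
| Target | 15/20/30/40 | 25.0 | 3.78 |
| Non-response scoring | 13.5/18.0/27.0/36.0 | 22.5 | 3.60 |
| Completers | 15.8/21.1/33.3/47.1 | 31.3 | 4.74 |
| Reason-specific | 15/20/30/40 | 25.0 | 3.78 |

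The completer odds ratio is (0.40/0.45)/(0.15/0.80) = 4.74. The two planned results differ by 31.3 − 22.5 = 8.8 points and lie on opposite sides of the target.

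**The case against.** Non-response scoring plus completers is a common pair in Phase 2. With equal missingness the rule attenuates the effect but creates no false positives, because equal rates stay equal. The planned comparison with placebo is an odds ratio, which moves little (3.78 to 3.45 at 20%). The size of the discontinuation problem is also undocumented. A participant who stops drug can still supply a Week 24 or ET biopsy (Protocol 8.5.1.1, 9.5.2.3). Protocol 6.3.2.1 and 6.3.2.3 report no earlier discontinuations for gastrointestinal or injection-related events. All of this stands. It limits the size of the concern but does not supply the missing analysis.

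A reader might infer three stronger points that the documents do not support.
- **That neither analysis is unbiased when biopsies are missed for unrelated reasons.** Case 1 shows that completers are then unbiased. The difficulty needs the mix.
- **That 37 of 197 (19%) missed their biopsy.** Those 37 are the difference between 197 randomised and the approximately 160 in the 29 May 2020 cut. Anyone randomised after mid-December 2019 would not have reached Week 24 by that date (24 weeks = 168 days), and a later biopsy up to Week 48 still counts.
- **That power falls below the stated 80%.** At 40 per arm the formula gives 79.5% at 15% missing and 76.6% at 20%, but 197 were randomised. The cut of about 160 already leaves out the other 37, so a 19% loss applied to 40 per arm removes them twice.

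**Conclusion.** The gap is real but modest. The plan has one rule that treats every absent biopsy as failure and one that drops every absent biopsy. It has none that separates stopping treatment from a biopsy never obtained for an unrelated reason. Under an assumed 5% to 20% of unrelated misses, equal across arms, non-response scoring takes 1.2 to 5.0 points off a 25-point difference. In the illustrative mix, the two planned results are 8.8 points apart with the target between them. The missing fractions and discontinuation rates are assumptions; the actual effect could be smaller, and would be nil if every participant on treatment was biopsied by Week 48. The validity of the primary test is not in question. This is an inexpensive improvement to the sensitivity analyses, not a reason to change the primary analysis.

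**What to change.** Keep non-response scoring as primary and the completer analysis as planned. Add one pre-specified sensitivity analysis to SAP 6.1.1.1:
- Participants who discontinued treatment without a biopsy remain non-responders.
- Participants on treatment whose biopsy was never obtained, and whose deviation carries the COVID-19 flag, are multiply imputed. Other missing biopsies stay non-responders.
- The imputation model is small: treatment arm, randomised stratum, baseline NAS, and one or two on-treatment markers available before Week 24, such as ALT or the Week 4-12 PRO-C3. Add MRE or MRI only where available, since a missed Week 24 visit may lose imaging too and Protocol 8.3.4 lets participants with contraindications enrol. Separate models per arm with many predictors would not be workable: 15% of 40 to 49 is about 6 to 7 expected placebo responders.
- The same Cochran-Armitage test and odds ratios are combined over imputations.

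In the same edit, reconcile SAP 7.2 with SAP 6.1.1. Section 7.2 invokes the mITT principle but describes the Week 24 efficacy set as participants whose biopsy is done, which leaves the non-responder rule with no one to act on at that lock. It should also say how a delayed biopsy still pending at the cut is treated.

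The cost is SAP wording and one program, using data already scheduled. The downside is one more model-based result, which assumes missing at random for the COVID-19-missed biopsies only.

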9.5.2.2 Secondary Efficacy Endpoints

Secondary endpoints will be analyzed using methodology consistent with that of the primary endpoint unless otherwise specified in the SAP.

Further details of the primary and secondary analyses, any additional sensitivity analyses and data handling details regarding issues such as missing data will be provided in the SAP.

9.5.2.3 Methods for Handling Treatment Discontinuations and Other Causes of Missing Data

Participants who prematurely discontinue study medication will be expected to complete an ET Visit and must continue to be followed for follow-up visits/procedures per the Schedule of Activities (e.g., Week 52/PTFU) (see [Section 1](#)).

Primary efficacy analyses will include all data that are collected on a participant during the study even after treatment discontinuation. All efficacy analyses will be performed with the mITT population, analyzed according to randomized treatment.

Additional details for handling of missing data will be provided in the SAP.

9.5.3 Safety Analyses

Safety analyses will be performed using the As Treated population. For analysis, all treatment-emergent (i.e., occurring after the first dose of study medication) AEs, SAEs, and AEs of special interest will be summarized by system organ class, preferred term, and treatment. Vital signs, immunogenicity, BMD, and laboratory data will be summarized by treatment. ECG abnormalities, physical examination abnormalities, if present, will be summarized.

Responses of anti-BMS-986036 antibodies and anti-FGF21 antibodies will be listed and tabulated by treatment and study day. The relationship between immunogenicity and PK and/or PD may be explored.

9.5.4 Pharmacokinetic Analysis

Trough BMS-986036 serum concentrations (in all participants at all visits) [REDACTED]

[REDACTED] will be summarized by treatment and visit.

The PK data obtained in this study may be combined with data from other studies of BMS-986036 to develop a population PK/PK-PD model. This model will be used to evaluate the effects of intrinsic and extrinsic (if applicable) covariates (e.g., immunogenicity and renal function) on the PK of BMS-986036 and to determine measures of individual exposure (such as peak, trough, and time-averaged concentration following a single dose) of BMS-986036. Model determined exposures will be used for exposure-response analyses of selected efficacy and safety endpoints, as appropriate. Details of the planned population PK and exposure-response analyses will be covered in a separate pharmacometric analysis plan and the results of the population PK and E-R analyses presented in a pharmacometric report, separate from the clinical study report.

9.5.5 Analyses of Exploratory Endpoints

Analyses for the exploratory efficacy endpoints will be described in the SAP, which will detail the derivation of the endpoints and associated statistical methods and models.

9.5.6 Interim Analysis

After approximately 100 participants have had their Week 24 biopsy assessments, an interim analysis may be performed for the purpose of internal decision making for future clinical development. The study will not be stopped on the basis of overwhelming efficacy and there is no plan to modify the design or the conduct of the study based on the results of this interim analysis. Analyses will be completed by pre-specified unblinded individuals. Details of the analysis will be provided in the SAP that will be finalized prior to this analysis.

9.5.7 Week 24 Data Analysis

[figure not shown]
Study data for all participants through Week 24 will be analyzed by pre-specified unblinded individuals when all participants have completed the liver biopsy at Week 24. Details of the analysis will be provided in the SAP that will be finalized prior to this Week 24 analysis.

11. APPENDICES

Appendix 1 Study Administrative Considerations

The term ‘participant’ is intended to refer to a person who has consented to participate in the clinical research study.

Regulatory and Ethical Considerations

Good Clinical Practice

This study will be conducted in accordance with:

- GCP guidelines
- as defined by ICH guidance
- in accordance with the ethical principles underlying European Union Directive 2001/20/EC
- United States Code of Federal Regulations, Title 21, Part 50 (21CFR50)
- applicable local requirements

The study will be conducted in compliance with the protocol. The protocol and any amendments and the participant informed consent will receive approval/favorable opinion by IRB/EC, and regulatory authorities according to applicable local regulations prior to initiation of the study.

All potential serious breaches must be reported to sponsor or designee immediately. A serious breach is a breach of the conditions and principles of GCP in connection with the study or the protocol, which is likely to affect, to a significant degree, the safety or physical or mental integrity of the participants of the study or the scientific value of the study.

Personnel involved in conducting this study will be qualified by education, training, and experience to perform their respective tasks.

This study will not use the services of study personnel where sanctions have been invoked or where there has been scientific misconduct or fraud (e.g., loss of medical licensure, debarment).

Institutional Review Board/Independent Ethics Committee

Before study initiation, the investigator must have written and dated approval/favorable opinion from the IRB/EC for the protocol, consent form, participant recruitment materials (e.g., advertisements), and any other written information to be provided to participants. The investigator or sponsor should also provide the IRB/EC with a copy of the IB or product labeling information to be provided to participants and any updates.

The investigator, sponsor or designee should provide the IRB/EC with reports, updates and other information (e.g., expedited safety reports, amendments, and administrative letters) according to regulatory requirements or institution procedures.

Compliance with the Protocol and Protocol Revisions

The investigator should not implement any deviation or change to the protocol without prior review and documented approval/favorable opinion of an amendment from the IRB/EC (and if applicable, also by local health authority) except where necessary to eliminate an immediate hazard(s) to study participants.

If a deviation or change to a protocol is implemented to eliminate an immediate hazard(s) prior to obtaining relevant approval/favorable opinion(s) the deviation or change will be submitted, as soon as possible to:

- IRB/EC
- Regulatory Authority(ies), if applicable by local regulations (per national requirements)

Documentation of approval/favorable opinion signed by the chairperson or designee of the IRB/EC(s) and if applicable, also by local health authority must be sent to the sponsor.

If an amendment substantially alters the study design or increases the potential risk to the participant: (1) the consent form must be revised and submitted to the IRB/EC(s) for review and approval/favorable opinion; (2) the revised form must be used to obtain consent from participants currently enrolled in the study if they are affected by the amendment; and (3) the new form must be used to obtain consent from new participants prior to enrollment.

If the revision is done via an administrative letter, investigators must inform their IRB/EC(s).

Financial Disclosure

Investigators and subinvestigators will provide the sponsor with sufficient, accurate financial information in accordance with local regulations to allow the sponsor to submit complete and accurate financial certification or disclosure statements to the appropriate health authorities. Investigators are responsible for providing information on financial interests during the course of the study and for 1 year after completion of the study.

[figure not shown]
Informed Consent Process

Investigators must ensure that participants are clearly and fully informed about the purpose, potential risks, and other critical issues regarding clinical studies in which they volunteer to participate.

In situations where consent cannot be given to participants, their legally acceptable representatives (as per country guidelines) are clearly and fully informed about the purpose, potential risks, and other critical issues regarding clinical studies in which the participant volunteers to participate.

The sponsor or designee will provide the investigator with an appropriate (i.e., global or local) sample ICF which will include all elements required by ICH, GCP, and applicable

regulatory requirements. The sample ICF will adhere to the ethical principles that have their origin in the Declaration of Helsinki.

Investigators must:

- Provide a copy of the ICF and written information about the study in the language in which the participant is most proficient prior to clinical study participation. The language must be nontechnical and easily understood
- Allow time necessary for participant or participant's legally acceptable representative to inquire about the details of the study
- Obtain an ICF signed and personally dated by the participant or the participant's legally acceptable representative and by the person who conducted the informed consent discussion.
- Obtain the IRB/EC's written approval/favorable opinion of the written ICF and any other information to be provided to the participants, prior to the beginning of the study, and after any revisions are completed for new information

If informed consent is initially given by a participant's legally acceptable representative or legal guardian, and the participant subsequently becomes capable of making and communicating his or her informed consent during the study, consent must additionally be obtained from the participant.

Revise the ICF whenever important new information becomes available that is relevant to the participant's consent. The investigator, or a person designated by the investigator, should fully inform the participant or the participant's legally acceptable representative or legal guardian, of all pertinent aspects of the study and of any new information relevant to the participant's willingness to continue participation in the study. This communication should be documented.

The confidentiality of records that could identify participants must be protected, respecting the privacy and confidentiality rules applicable to regulatory requirements, the participants' signed ICF and, in the United States, the participants' signed Health Insurance Portability and Accountability Act Authorization.

The consent form must also include a statement that the sponsor and regulatory authorities have direct access to participant records.

Participants unable to give their written consent (e.g., those with stroke or severe dementia) may only be enrolled in the study with the consent of a legally acceptable representative. The participant must also be informed about the nature of the study to the extent compatible with his or her understanding, and should this participant become capable, he or she should personally sign and date the consent form as soon as possible. The explicit wish of a participant who is unable to give his or her written consent, but who is capable of forming an opinion and assessing information to refuse participation in, or to be withdrawn from, the clinical study at any time should be considered by the investigator.

The rights, safety, and well-being of the study participants are the most important considerations and should prevail over interests of science and society.

Source Documents

The investigator is responsible for ensuring that the source data are accurate, legible, contemporaneous, original, and attributable, whether the data are hand-written on paper or entered electronically. If source data are created (first entered), modified, maintained, archived, retrieved, or transmitted electronically via computerized systems (and/or any other kind of electronic devices) as part of regulated clinical study activities, such systems must be compliant with all applicable laws and regulations governing use of electronic records and/or electronic signatures. Such systems may include, but are not limited to, electronic medical/health records (EMRs/EHRs), AE tracking/reporting, protocol-required assessments, and/or drug accountability records.

When paper records from such systems are used in place of electronic format to perform regulated activities, such paper records should be certified copies. A certified copy consists of a copy of original information that has been verified, as indicated by a dated signature, as an exact copy having all of the same attributes and information as the original.

Study Medication Records

The study personnel will account for all study medications dispensed to and returned from the participant. Study site personnel will account for all unused study medications at the site, and unused study medication will be destroyed at the site or returned to the sponsor or designee for appropriate destruction, depending on circumstances. Records for study medications (whether supplied by the sponsor, its vendors, or the site) must substantiate study medication integrity and traceability from receipt, preparation, administration, and through destruction or return. Records will be reconciled with existing study medication by a study monitor prior to destruction of the product. Certificates of destruction should be signed and will be included in the Trial Master File. Records must be made available for review at the request of sponsor/designee or a health authority.

If	Then
Supplied by the sponsor (or its vendors):	
Records or logs must comply with applicable regulations and guidelines and should include:
 
• amount received and placed in storage area• amount currently in storage area• label identification number or batch number• amount dispensed to and returned by each participant, including unique participant identifiers• amount transferred to another area/site for dispensing or storage• nonstudy disposition (e.g., lost, wasted)• amount returned to the sponsor or designee• retain samples for bioavailability/bioequivalence, if applicable• dates and initials of person responsible for Investigational Product dispensing/accountability, as per the Delegation of Authority Form.

The sponsor or designee will provide forms to facilitate inventory control if the investigational site does not have an established system that meets these requirements.

Case Report Forms

An investigator is required to prepare and maintain adequate and accurate case histories designed to record all observations and other data pertinent to the investigation on each individual treated or entered as a control in the investigation. Data that are derived from source documents and reported on the eCRF must be consistent with the source documents or the discrepancies must be explained. Additional clinical information may be collected and analyzed in an effort to enhance understanding of product safety. eCRFs may be requested for AEs and/or laboratory abnormalities that are reported or identified during the course of the study.

For sites using the sponsor or designee electronic data capture (EDC) tool, eCRFs will be prepared for all data collection fields with the exclusion of data collection associated with pregnancy, which will be reported on the Pregnancy Surveillance Form. Spaces may be left blank only in those circumstances permitted by study-specific eCRF completion guidelines provided by sponsor or designee.

The confidentiality of records that could identify participants must be protected, respecting the privacy and confidentiality rules in accordance with the applicable regulatory requirement(s).

The investigator will maintain a signature sheet to document signatures and initials of all persons authorized to make entries and/or corrections on eCRFs.

The completed eCRF and SAE/pregnancy eCRFs, must be promptly reviewed, signed, and dated by the investigator or qualified physician who is a subinvestigator and who is delegated this task on the Delegation of Authority Form. Subinvestigators in Japan may not be delegated the eCRF approval task. For eCRFs, review and approval/signature should be completed electronically through the study EDC tool. The investigator must retain a copy of the eCRFs including records of the changes and corrections.

Each individual electronically signing electronic eCRFs must meet sponsor or designee training requirements and must only access the study EDC tool using the unique user account provided by sponsor or designee. User accounts are not to be shared or reassigned to other individuals.

Monitoring

The sponsor or designee representatives will review data centrally to identify potential issues to determine a schedule of on-site visits for targeted review of study records.

Representatives of the sponsor or designee must be allowed to visit all study site locations periodically to assess the data quality and study integrity. On site, they will review study records and directly compare them with source documents, discuss the conduct of the study with the investigator, and verify that the facilities remain acceptable. Certain eCRF pages and/or electronic files may serve as the source documents.

In addition, the study may be evaluated by the sponsor or designee internal auditors and government inspectors who must be allowed access to case report forms, source documents, other study files, and study facilities. The sponsor audit reports will be kept confidential.

The investigator must notify the sponsor promptly of any inspections scheduled by regulatory authorities, and promptly forward copies of inspection reports to sponsor or designee.

Records Retention

The investigator (or head of the study site in Japan) must retain all study records and source documents for the maximum period required by applicable regulations and guidelines, or institution procedures, or for the period specified by the sponsor or designee, whichever is longer. The investigator (or head of the study site in Japan) must contact the sponsor prior to destroying any records associated with the study.

The sponsor or designee will notify the investigator (or head of the study site in Japan) when the study records are no longer needed.

If the investigator withdraws from the study (e.g., relocation, retirement), the records shall be transferred to a mutually agreed upon designee (e.g., another investigator, study site, IRB/EC). Notice of such transfer will be given in writing to the sponsor or designee.

Return of Study Medication

For this study, study medications (those supplied by the sponsor, a vendor, or sourced by the investigator) such as partially used study medication containers and syringes may be destroyed on site (as applicable; some sites will return unused study medications depending on circumstances).

If ...	Then
Study medications supplied by the sponsor (including its vendors)	
Any unused study medications supplied by the sponsor can only be destroyed after being inspected and reconciled by the responsible study monitor unless study medications containers must be immediately destroyed as required for safety, or to meet local regulations (e.g., cytotoxics or biologics).
 
If study medications will be returned, the return will be arranged by the responsible study monitor.

It is the investigator's or designee's responsibility to arrange for disposal, provided that procedures for proper disposal have been established according to applicable federal, state, local, and institutional guidelines and procedures, and provided that appropriate records of disposal are kept. The following minimal standards must be met:

- On-site disposal practices must not expose humans to risks from the drug
- On-site disposal practices and procedures are in agreement with applicable laws and regulations, including any special requirements for controlled or hazardous substances
- Written procedures for on-site disposal are available and followed. The procedures must be filed with the site's standard operating procedures and a copy provided to the sponsor upon request
- Records are maintained that allow for traceability of each container, including the date disposed, quantity disposed, and identification of the person disposing the containers. The method of disposal (e.g., incinerator, licensed sanitary landfill, or licensed waste disposal vendor) must be documented
- Accountability and disposal records are complete, up-to-date, and available for the study monitor to review throughout the clinical study period

It is the investigator's or designee's responsibility to arrange for disposal of all empty containers.

If conditions for destruction cannot be met, the responsible study monitor will make arrangements for return of study medications provided by the sponsor (or its vendors). Destruction of nonstudy medications sourced by the site, not supplied by the sponsor, is solely the responsibility of the investigator or designee.

For sites that will not destroy study medication on site, it is the investigator's or designee's responsibility to arrange for disposal of all empty study medication containers, provided that procedures for proper disposal have been established according to applicable federal, state, local, and institutional guidelines and procedures, and provided that appropriate records of disposal are kept. The return of full or partially used study medications supplied by the sponsor or its vendors will be arranged by the responsible study monitor.

Clinical Study Report and Publications

A signatory investigator must be selected to sign the clinical study report. For this protocol, the signatory investigator will be selected as appropriate based on one or more of the following criteria:

- External principal investigator designated at protocol development
- National coordinating investigator
- Participant recruitment (e.g., among the top quartile of enrollers)
- Involvement in study design
- Regional representation (e.g., among top quartile of enrollers from a specified region or country)
- Other criteria (as determined by the study team)

The data collected during this study are confidential and proprietary to sponsor or designee. Any publications or abstracts arising from this study must adhere to the publication requirements set forth in the clinical study agreement (CTA) governing study site or investigator participation in the study. These requirements include, but are not limited to, submitting proposed publications to sponsor or designee at the earliest practicable time prior to submission or presentation and otherwise within the time period set forth in the CTA.

Data Monitoring Committee

This study will utilize a DMC for the duration of the study. Additional details can be found in the DMC charter and will be provided upon request.

Appendix 2

Women of Childbearing Potential Definitions and Methods of Contraception

Definitions

Woman of Childbearing Potential

A woman is considered fertile following menarche and until becoming postmenopausal unless permanently sterile. Permanent sterilization methods include hysterectomy, bilateral salpingectomy, and bilateral oophorectomy.

Women in the following categories are not considered WOCBPs:

- Premenarchal
- Premenopausal female with 1 of the following:
 - Documented hysterectomy
 - Documented bilateral salpingectomy
 - Documented bilateral oophorectomy

Note: Documentation can come from the site personnel's review of the participant's medical records, medical examination, or medical history interview.

- Postmenopausal female
 - A postmenopausal state is defined as 12 months of amenorrhea in a woman over age 45 years in the absence of other biological or physiological causes. In addition, females under the age of 55 years must have a serum follicle stimulating hormone (FSH) level > 40 mIU/mL to confirm menopause.

Note: Females treated with hormone replacement therapy (HRT) are likely to have artificially suppressed FSH levels and may require a washout period in order to obtain a physiologic FSH level. The duration of the washout period is a function of the type of HRT used. The duration of the washout periods below are suggested guidelines and the investigators should use their judgment in checking serum FSH levels.

- 1 week minimum for vaginal hormonal products (rings, creams, gels)
- 4 week minimum for transdermal products
- 8 week minimum for oral products

